8.3 Premature Subject Withdrawal

All subjects will be advised that they are free to withdraw from participation in this study at any time, for any reason, and without prejudice. Subjects must be withdrawn from the study if they withdraw consent to participate. Investigators must attempt to contact subjects who fail to attend scheduled visits by telephone or other means to exclude the possibility of an AE being the cause of withdrawal. Should this be the cause, the AE must be documented, reported, and followed as described in Section 11.2.

The sponsor reserves the right to request the withdrawal of a subject due to protocol deviations or other reasons.

The investigator also has the right to withdraw subjects from the study at any time for lack of therapeutic effect that is intolerable or otherwise unacceptable to the subject, for intolerable or unacceptable AEs, intercurrent illness, noncompliance with study procedures, administrative reasons, or in the investigator's opinion, to protect the subject's best interest.

If a subject is withdrawn before completing the study, the reason for withdrawal and the date of discontinuation will be recorded on the appropriate page of the case report form (CRF) or electronic case report form (eCRF). Whenever possible and reasonable, the evaluations that were to be conducted at the completion of the study should be performed at the time of premature discontinuation.

A participant will be considered lost to follow-up if he or she fails to return for scheduled visits and is unable to be contacted by the study site staff.

The following actions must be taken if a participant fails to return to the clinic for a required study visit:

- The site will attempt to contact the participant and reschedule the missed visit and counsel the participant on the importance of maintaining the assigned visit schedule and ascertain if the participant wishes to and/or should continue in the study.
- Before a participant is deemed lost to follow-up, the investigator or designee will make every effort to regain contact with the participant (where possible, 3 telephone calls and, if necessary, a certified letter to the participant's last known mailing address or local equivalent methods). These contact attempts should be documented in the participant's medical record or study file.

• Should the participant continue to be unreachable, he or she will be considered to have withdrawn from the study with a primary reason of lost to follow-up.

Subject Replacement Criteria

Withdrawn subjects may be replaced if withdrawal occurs at, or prior to, the Week 2 visit.

9 TREATMENTS

9.1 Identification of Investigational Products

The products that will be used in this study are outlined in Table 9-1.

Table 9-1: Identification of Investigational Product

Product	Strength and dosage form	Manufacturer/Supplier
MEDI7352	CCI	
Solvent for reconstitution of MEDI7352		
Diluent for reconstituted MEDI7352 and placebo		
IV bag protectant		
CCI		

9.1.1 Dose, Route of Administration, and Dosing Schedule

Once randomized, subjects will be dosed with either MEDI7352 or placebo on Day 1, Day 14, Day 28, Day 42, Day 56, and Day 70. MEDI7352 or placebo will be administered IV over a 60-minute period.

MEDI7352 or placebo should be administered by the investigator or site personnel prepared to manage infusion reactions and anaphylaxis. The infusion rate may be slowed or interrupted if the subject develops an infusion reaction. [NOTE: If the infusion is slowed or interrupted, the total infusion time should not exceed 4 hours at room temperature.] Investigators/site personnel should be aware of the risk of hypersensitivity reactions, which may present as infusion reactions, and monitor subjects closely. In the event of a serious reaction, MEDI7352 or placebo administration must be discontinued immediately and the appropriate medical therapy administered.

Subjects will be dosed as outpatients but should remain under clinical supervision and should be monitored for no less than 4 hours after completion of each infusion. Should clinical features of acute hypersensitivity occur, an extended period of monitoring in an appropriate environment may be relevant, based on clinical judgement. This may include, but is not necessarily limited to, monitoring vital signs and observing for any untoward reactions. Consultation with the appropriate local clinical services may be warranted (eg, high dependency or intensive therapy unit).

Subjects should be made aware of the potential risks of acute hypersensitivity and infusion-related reactions, the signs and symptoms of such reactions, and the importance of immediately seeking medical attention should they occur.

9.1.2 Current Treatment of Painful Diabetic Neuropathy

Subjects should currently be taking medication for the treatment of PDN. Subjects should be taking at least one of the first-line medications (consistent with regional or local standard of care guidelines for PDN) belonging to *either* the anticonvulsant class (pregabalin or gabapentin) *or* the antidepressant class (duloxetine, venlafaxine, or amitriptyline), but no more than one medication from a single class. Subjects receiving treatment with opioids alone (as a monotherapy) should be excluded, *unless* the opioids are being prescribed as a second-line treatment for PDN because the first-line therapies were found to be poorly tolerated or not efficacious. For all drug classes, subjects should be established on a stable dosing regimen that is consistent with regional or local standards of accepted prescribing practice for no less than 3 months before the anticipated randomisation date. Subjects should be willing to maintain this stable dosing regimen for the duration of study participation until the last follow-up visit.

9.1.3 Rescue Medication

13-Apr-2022

Subjects who develop unacceptable pain during any stage of the study (including during the washout period prior to randomisation) will be permitted to initiate rescue analgesic therapy with paracetamol up to a maximum dose of two 500 mg tablets (ie, 1 g per dose) up to 4 times daily (ie, 4 g per 24-hour period).

If paracetamol does not relieve the subject's pain, they may receive stronger analgesics as rescue medication (including tramadol and other 'weak' opiates) at the investigator's discretion and in consultation with the medical monitor.

Subjects may use sedative/hypnotics (eg, benzodiazepines) on a pro re nata (PRN; where necessary) basis, but these should not be taken more than 3 times a week or within 24 hours of a

clinic visit and such use will be considered a protocol deviation. Prohibited therapies are listed in Section 9.7.2. Other restrictions are listed in Section 9.7.3.

As a guideline, rescue medication should not generally be given for more than 3 consecutive days. All rescue medication use must be captured in the CRF and subjects will be required to record reasons for use.

The study site will not supply rescue medication.

The date and time of rescue medication administration as well as the name and dosage regimen of the rescue medication must be recorded.

9.2 Selection of Timing of Dose for Each Subject

The 2-weekly dose interval has been chosen based on PK, PD (NGF suppression) and efficacy considerations. In the first-in-human study in subjects with OA, the dosing schedule was 2-weekly, and preliminary (blinded) data indicated that the effect of MEDI7352 on OA pain was detectable for 2 weeks.

9.3 Dose Adjustment Criteria

Dose adjustment is not allowed in this study. Subjects will be allocated to a single dosing regimen at randomisation.

9.3.1 Safety Stopping Rules

Safety will be monitored by the study-appointed medical monitors from Premier Research and AstraZeneca throughout the study in accordance with the Medical Monitoring Plan. In addition, an Interim Safety Review of blinded aggregate safety data will be undertaken following completion of follow-up visits for approximately every 30 subjects enrolled in the study and no less frequently than every 3 months. The interim review will be performed by AstraZeneca Neuroscience in conjunction with the pharmacovigilance and safety agent, MMS Holdings in accordance with the Safety Management Plan.

Based on the interim safety reviews of aggregate safety data, the study may be stopped if the risks are found to outweigh the potential benefits.

For any individual subject, further administration of IP will be stopped if any of the following scenarios occur with a reasonable possibility of a causal relationship to administration of MEDI7352:

- Reports of drug-related serious AE (SAE[s]) or drug-related severe AE(s) including (but not necessarily limited to):
 - o Infusion reactions and injection site reactions
 - Worsening of existing cutaneous sensory abnormalities or development of new cutaneous sensation AEs (eg, paraesthesia, dysesthesia, burning, pins and needles) that are considered serious or severe and drug-related
 - o Positively adjudicated destructive arthropathy
 - o Serious systemic infection

AD-MW-07.06 08-Dec-2017 722 of 938 Page 49 of 114

- Anaphylactic reaction, defined as an immediately life-threatening allergic reaction with bronchoconstriction, angioedema, and/or hypotension (refer to FDA Guidance for Industry, Immunogenicity assessment for therapeutic protein products, 2014).⁴²
- o Fulfilling Hy's Law, defined as AST or ALT $\ge 3 \times \text{ULN}$ and bilirubin $\ge 2 \times \text{ULN}$, in the absence of a significant increase in alkaline phosphatase (ALP) and in the absence of an alternative diagnosis that could explain the increase in bilirubin
- O Severe autonomic AEs, including but not limited to symptomatic orthostatic hypotension and orthostatic intolerance, that are considered drug-related
- o Renal toxicity, defined as serum creatinine $\geq 1.5 \times \text{ULN}$
- o Haematologic toxicity, defined as one or more of the following:
 - Leukocyte count $< 2.0 \times 10^9/L$
 - Neutrophil count $<1.0 \times 10^9/L$
 - Platelet count $< 75 \times 10^9 / L$

9.4 Treatment Compliance

All subjects will receive the IP infusion at the study site under the surveillance of appropriate study personnel. Infusion details will be recorded in the subject's eCRF.

9.5 Method of Assigning Subjects to Treatment Groups

The randomisation schedule will be computer generated using a permuted block algorithm appropriate to the treatment groups included in each stage and will randomly allocate IP to randomisation numbers. The randomisation numbers will be assigned sequentially through a central interactive web response system (IWRS) as subjects are entered into the study. The randomisation schedule will not be stratified and study center will not be a blocking factor in the randomisation schedule.

The randomisation schedule will be prepared by Premier Research before the start of the study. No one involved in the study performance will have access to the randomisation schedule before official unblinding of treatment assignment. No subject will be randomised into this study more than once.

9.6 Blinding and Unblinding Treatment Assignment

All subjects, investigators, and study personnel involved in the conduct of the study, including data management, will be blinded to treatment assignment with the exception of a specified unblinded statistician and programmer from Premier Research who will have access to the randomization code, unblinded site monitors and clinical manager from Premier Research, and the unblinded pharmacist at each study site. The unblinded study personnel will not participate in study procedures or data analysis prior to unblinding of the study data to all study-related personnel. Unblinded personnel who are not otherwise involved in the study will prepare data for review and interim analysis.

Study personnel will make every effort to safeguard the integrity of the study blind to minimize bias in the conduct of the study. Treatment unblinding is discouraged if knowledge of the treatment assignment will not materially change the planned management of a medical emergency. Unblinding will be permitted in a medical emergency that requires immediate knowledge of the subject's treatment assignment.

Unblinding should be discussed in advance with the medical monitor if possible. For emergency unblinding, study personnel will use the IWRS. Only authorized users will have access to the unblinding function in the IWRS, and the IWRS will reveal the treatment information for the selected subject only. If the investigator is not able to discuss treatment unblinding in advance, then he/she must notify the medical monitor as soon as possible about the unblinding incident without revealing the subject's treatment assignment. The IWRS will also send a blinded notification to the clinical team alerting them that a break blind occurred.

The investigator or designee must record the date and reason for treatment unblinding on the appropriate CRF for that subject. In all cases that are not emergencies, the investigator must discuss the event with the medical monitor prior to unblinding the subject's treatment assignment.

If treatment assignment is unblinded for an individual subject, study personnel will be notified of that subject's treatment assignment without unblinding the treatment assignments for the remaining subjects in the study. Thus, the overall study blind will not be compromised. If a subject's treatment assignment is unblinded, he/she will be asked to withdraw from the study. The investigator will make this decision after consultation with the medical monitor.

Overall unblinding will take place at the end of the study only after database lock has been achieved.

9.7 **Permitted and Prohibited Therapies**

All concomitant medications used (including OTC medications and herbal supplements) will be recorded in the source document and on the appropriate eCRF.

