10.2.3 Follow-up (or Early Termination) Evaluation (Week 18)

At 6 weeks after the last visit (8 weeks after the last administration of the IP) or upon early termination of the study, the following procedures will be performed:

- 1. Perform Galer NPS.
- 2. Perform PGIC.
- 3. Perform a complete physical and neurological examination (excluding the genitourinary examination, unless warranted).
- 4. Perform TNSn, strength (dorsiflexion), and deep tendon reflex (knee and ankle) assessments.
- 5. Perform 3 replicates of 12-lead ECGs (with printouts) after the subject has been resting in the supine position for at least 10 minutes.
- 6. Perform motor and sensory NCS.
- 7. Collect blood samples for the following:
 - chemistry, haematology, and coagulation

AD-MW-07.06 08-Dec-2017 733 of 938 Page 60 of 114

- immunogenicity (ADA) testing
- PK and CCI (only if this is an Early Termination Visit)
- 8. Collect urine sample for the following:
 - urinalysis
 - urine pregnancy test (for women who are not surgically sterile)

- 9. Measure sitting vital signs (HR, BP [sitting after a 5-minute rest], respiratory rate, and temperature). To assess orthostasis, repeat the measurement of BP and pulse 1 (>1 minute, <3 minutes) minute after the subject stands.
- 10. Assess the IV injection site for local reactions.
- 11. Record AEs and concomitant medications and therapies.

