11.2 Event Assessment and Follow-up of Adverse Events

The occurrence of an AE or SAE may come to the attention of study personnel during study visits and interviews of a study participant presenting for medical care, or upon review by a study monitor.

All AEs including local and systemic reactions not meeting the criteria for SAEs will be captured on the appropriate eCRF. Information to be collected includes event description, time of onset, clinician's assessment of severity, relationship to study product (assessed only by those with the training and authority to make a diagnosis), and time of resolution/stabilization of the event. All AEs occurring while on study must be documented appropriately regardless of relationship. All AEs will be followed to adequate resolution.

Any medical condition that is present at the time that the participant is screened will be considered as baseline and not reported as an AE. However, if the study participant's condition deteriorates at any time during the study, it will be recorded as an AE.

Changes in the severity of an AE will be documented to allow an assessment of the duration of the event at each level of severity to be performed. AEs characterized as intermittent require documentation of onset and duration of each episode.

The site staff will record all reportable events with start dates occurring any time after informed consent is obtained until 7 (for nonserious AEs) or 30 days (for SAEs) after the last day of study participation. At each study visit, the investigator will inquire about the occurrence of AE/SAEs since the last visit. Events will be followed for outcome information until resolution or stabilization.

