13.1.6.1 Adverse Events

All AEs will be coded using the latest version of the Medical Dictionary for Regulatory Activities (MedDRA).

Treatment-emergent AEs are defined as:

- AEs with onset at the time of or following the start of treatment with IP through the Follow-up Visit or Early Termination Visit, whichever occurs first, or
- AEs starting prior to the start of treatment but increasing in severity or relationship at the time of, or following, the start of treatment with IP through the Follow-up Visit or Early Termination Visit, whichever occurs first.

The number and percentage of subjects with AEs will be displayed for each treatment group by system organ class and preferred term (PT). Summaries of AEs by severity and relationship to IP will also be provided. Serious adverse events and AEs resulting in discontinuation of IP will be summarized separately in a similar manner. Subject listings of AEs, SAEs, and AEs causing discontinuation of IP will be produced.

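### Section 9.6 asks unblinded subjects to leave the study and does not separate this from stopping study drug, so scheduled safety follow-up is shortened and the pain diary stops

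*Protocol*

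**What the plan says.** Section 9.6 permits unblinding mainly for emergencies: "Unblinding will be permitted in a medical emergency that requires immediate knowledge of the subject's treatment assignment". It also foresees other cases: "In all cases that are not emergencies, the investigator must discuss the event with the medical monitor prior to unblinding the subject's treatment assignment". For any unblinded subject it then says "If a subject's treatment assignment is unblinded, he/she will be asked to withdraw from the study", followed by "The investigator will make this decision after consultation with the medical monitor". It gives no criteria for that decision, and no arrangement for staying under observation without study drug.

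Several other sections govern what happens once a subject leaves:

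- **Section 8.3:** where feasible, the end-of-study evaluations are done when the subject leaves early.
- **Section 10.2.3:** the Week 18 procedures are carried out at Week 18 "or upon early termination of the study, the following procedures will be performed".
- **Section 11.2:** new events are recorded "until 7 (for nonserious AEs) or 30 days (for SAEs) after the last day of study participation". Sections 11.2 and 11.2.5 keep events already recorded under follow-up until they resolve or are stable.
- **Section 11.2.6.2:** suspected serious adverse drug reactions are reportable with no time limit.
- **Section 13.1.4:** a missing Week 12 pain score is filled by LOCF for the main analysis.
- **Sections 11.1.6 and 13.1.6.1:** these define the treatment-emergent window differently. The first runs to 30 days after the last dose. The second runs "through the Follow-up Visit or Early Termination Visit, whichever occurs first".

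**The concern.** Leaving a study and stopping its drug are different things. Section 9.3.1 treats them so: its individual stopping rules halt further IP and do not mention withdrawal from the study. Section 9.6 goes straight to study withdrawal.

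The subjects affected are selected by something that happened after randomisation, usually a medical emergency, and possibly unevenly by arm. For them the plan stops collecting two kinds of data that the subject might have been willing to give.

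- **Safety:** later scheduled neuropathy scores (TNSn), laboratory tests and the Week 18 visit are lost. Section 5.3 relies on peripheral nerve monitoring, including nerve conduction studies, to manage the neuropathy risk. The only nerve conduction study after baseline is at follow-up or early termination, so early exit brings it forward.
- **Pain:** the diary stops, and the Week 12 value becomes a carried-forward one for a reason likely to be informative.

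There is no data safety monitoring board (Section 12), and the interim safety reviews use blinded aggregate data (Section 9.3.1). That raises the value of full follow-up in subjects with serious events.

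**Working it through.** There is no stated figure to reproduce, because the point rests on how the sections fit together. The arithmetic below sizes the gap.

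**1. Scheduled follow-up lost**

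Inputs: Week 18 is nominal Day 18 × 7 = 126 (Table 2-1). The collection window for serious events after exit is 30 days (Section 11.2). I assume that the exit visit falls on the day of unblinding and is the last day of participation.

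- Days lost = 126 − exit day.
- Days lost beyond the serious-event window = 126 − exit day − 30.

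| Exit day | Scheduled follow-up lost | Of which beyond 30 days |
|---|---|---|
| 1 | 125 | 95 |
| 42 | 84 | 54 |
| 70 (last dose) | 56 | 26 |

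For nonserious events the window is 7 days, so after a Day 42 exit 84 − 7 = 77 days have no planned collection of new events.

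**2. What still runs after exit**

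The exit visit carries the Week 18 procedures, including TNSn, ECG, nerve conduction, laboratory tests and anti-drug antibodies. The event that prompted unblinding stays under follow-up. Suspected serious adverse drug reactions remain reportable. A serious event is therefore missed only if it is new, starts more than 30 days after exit and is not suspected to be drug-related.

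**3. Treatment-emergent status**

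Take a last dose and exit both on Day 42. Section 11.1.6 keeps the window open to Day 42 + 30 = 72. Section 13.1.6.1 closes it on Day 42. A serious event on Day 60 would be collected and would be treatment-emergent under the first definition but not the second.

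If the same subject stayed to Week 18 with no further dose, the windows would end on Day 72 and Day 126. The two definitions disagree either way.

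**4. Primary endpoint**

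A Day 42 exit leaves 84 − 42 = 42 days without diary data before Week 12. The unblinding rate is not given. Assuming 1% to 2% of 272 randomised subjects gives 2.7 to 5.4, or about 3 to 5.

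Suppose all five were among the 236 evaluable subjects. Each point of average error in their carried-forward scores would move the overall mean by 5/236 = 0.02 points. If all five fell in the smallest evaluable group (37), it would move that group's mean by 5/37 = 0.14. The planned difference is 1.25.

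**The case against.** The strongest reply is that the protocol already protects these subjects. The event behind the unblinding is followed to its outcome, a full exit visit is planned, serious events are captured for a further 30 days, and withdrawal is a request judged case by case. All of that stands. A reader might infer from the quoted sentence that safety follow-up ends when an emergency occurs, or that removal is automatic. The documents do not support either reading.

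A reader might also infer that events after exit can never count as treatment-emergent. That follows only from Section 13.1.6.1. Section 11.1.6 has no link to the early termination visit.

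A second reply is that diary data stop after every withdrawal under Section 8.3, at an anticipated overall rate of about 10%, and that pain scores given with knowledge of treatment are the least interpretable. This is fair, and it is why those scores should not enter the main analysis. It is no reason to leave them uncollected, because a flagged score can be set aside later and an uncollected one cannot be recovered. Laboratory and nerve conduction results are less open to that bias. Section 9.6 also differs from the general case, because here the plan itself prompts the exit.

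A third reply is that no other text in Section 9.6 takes an unblinded subject off IP, so replacing the sentence alone would leave dosing undefined. This is correct, and the remedy has to deal with it.

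**Conclusion.** The point holds in a limited form. Section 9.6 makes leaving the study the default after any unblinding and does not treat study drug as a separate question. The cost is the scheduled safety monitoring after exit, new nonserious events after 7 days, new serious events after 30 days unless they are suspected drug reactions, and observed pain up to Week 12. A Day 42 exit loses 84 scheduled days, 54 of them beyond the serious-event window.

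The number of subjects is unknown. At an assumed 1% to 2% it is about 3 to 5, so the effect on the primary estimate is minor. This is a worthwhile improvement and does not threaten the trial's main conclusion. The day counts rest on nominal visit days and on exit on the day of unblinding.

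**What to change.** In Section 9.6, replace the request to withdraw with a statement that an unblinded subject is asked to remain for the already scheduled safety assessments and pain diary through Week 18, unless consent is withdrawn.

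Flag pain scores recorded after unblinding. Leave the main analysis as planned, with carry-forward drawing only on entries made before unblinding, and use the flagged scores in a sensitivity analysis.

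Two companion changes are needed:

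- The sponsor should state separately how IP is handled after unblinding, since Section 9.6 does not say. This review takes no position on what that rule should be.
- Sections 11.1.6 and 13.1.6.1 should be reconciled to a single treatment-emergent window.

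The cost is a few sentences and the remaining scheduled visits for what are probably a few subjects. The drawback is that pain scores after unblinding may be influenced by knowledge of treatment. Flagging them and keeping them out of the main analysis contains that.
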